⁴ A difference in VT of 1 ml O₂/kg/min is justified as being clinically significant based on prior studies of cardiac resynchronization therapy showing that there is an approximately 1 ml O₂/kg/min change in response to that approved therapy (Auricchio et al. J Am Coll Cardiol 2003;42:2109-16)

The secondary analyses will include:

- a. Comparison between groups of the change from baseline in New York Heart Association (NYHA) classification. NYHA classification shall be assigned by:
 - i. blinded on site clinicians according to their standard clinical practice
 - ii. by a blinded core lab that evaluates patient responses to a standardized questionnaire.⁵
- b. Comparison between groups of the changes from baseline in quality of life, as assessed by the Minnesota Living with Heart Failure (MLWHF) Questionnaire.
- c. Comparison between groups of the change from baseline in exercise tolerance, as quantified by the six minute hall walk test (6MW).
- d. Comparison between groups of the change from baseline in left ventricular ejection fraction as assessed by echocardiography in a blinded core lab.
- e. Comparison between groups of the change from baseline in left ventricular size as indexed by echocardiographically determined end-diastolic dimension determined by a blinded core lab.
- f. Comparison between groups of the change from baseline in peak VO₂ and ventilatory efficiency determined on CPX testing.
- g. Comparisons of treatment effects separately in subjects whose CHF etiology is ischemic or non-ischemic
- h. Comparison between groups of the change from baseline in medical treatment for heart failure (either up or down titration of doses or changes in the types of medications prescribed).

⁵ **Kubo SH, Schulman S, Starling RC, Jessup M, Wentworth D and Burkhoff D.** Development and validation of a patient questionnaire to determine New York Heart Association classification. *J Card Fail* 10: 228-235, 2004.

- i. Comparison within the treatment group of the primary and secondary safety and efficacy outcome measures in subjects with and without a pacemaker or ICD.
 - j. Evaluation of the impact of CCM voltage on primary and secondary efficacy and safety outcome measures.
5. Other Analyses

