Fourteen of the patients who participated in the study described in (3) above participated in a second clinical study to investigate the effects of increased duration of CCM treatment. In these subjects, the OPTIMIZER II device was programmed to deliver CCM signal for 7 noncontiguous hours per day (7 cycles of 1 hour on, 2 hours 24 minutes off) for 6 months. Upon entry into this increased dose safety study, the clinical status was markedly improved compared to their original baseline status prior to having received CCM treatment. NYHA averaged 1.6 ± 0.5 , MLWHFQ averaged 9.6 ± 6.2 , 6MW averaged 471 ± 121 , peak VO₂ averaged 1065 ± 215 ml O₂/min ($\sim 14.0 \pm 2.8$ ml O₂/kg/min) and ejection fraction averaged $35 \pm 9\%$. Over the 24 week follow-up period, the clinical parameters were maintained at relatively constant levels, except for peak VO₂ which increased to 1201 ± 343 ml O₂/min (15.8 ± 4.5 ml O₂/kg/min; $p=0.02$). Medical therapy for heart failure did not change in a majority of patients during this study, and there was an approximately equal number of instances when medication use was increased as when it was decreased.

During the 8 week period of the original FIX-HF-3 study described above, there were 43 adverse events reported in these 14 study subjects. Ten of these events were classified as serious and/or severe. Twelve of the events were classified by the investigators as being definitely, possibly or probably related to

the device. In contrast, during the 24 week period of the present FIX-HF-3 Extension study, there were a total of 43 adverse events of which three were classified as serious and 14 were classified as being definitely, possibly or probably related to the device. Thus, the rate (number of AEs/time) and severity (number of serious AEs) of adverse events was significantly lower in the FIX-HF-3 Extension study than in the original FIX-HF-3 study. The most common adverse events reported during the FIX-HF-3 Extension study were palpitations, dyspnea and pulmonary edema, which are similar to what was reported in the original FIX-HF-3 study.

In aggregate, these results suggest that the OPTIMIZER™ System operates as intended, and appears to be safe when set to deliver CCM pulses for 7 hours/day and that further study of the OPTIMIZER II system in patients with chronic heart failure within the context of randomized, blinded trials to rigorously evaluate the safety and efficacy of this form of treatment are warranted.

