This is a multicenter, prospective, randomized, study in 418 subjects with moderate to severe heart failure despite optimal medical therapy. The study will include a baseline eligibility evaluation followed by randomization to either receive or not receive an OPTIMIZER™ device implant. All patients will be followed for twelve-months (**Figure 1**). Evaluation of subjects will be documented on electronic case report forms and will include the tests and procedures listed in **Table 1**.

FIGURE 1. Study Overview

[figure not shown]

TABLE 1. Schedule of Events

Test	Screening	Baseline	Implant*	Follow-Up Schedule (relative to Study Start Date [§])						
				Week 2 ±2 days [§]	+4±1 Week	+12±2 Weeks	+24±2 Weeks	36±2 Weeks	50±2 Weeks	Every 6 Months*
Informed Consent	X									
History	X			X	X	X	X	X	X	X
NYHA Class (Blinded site clinician assessment)	X					X	X		X	
NYHA Class (Blinded Core Lab Questionnaire)	X					X	X		X	
Medications	X			X	X	X	X	X	X	
Physical Examination	X			X	X	X	X	X	X	
12-Lead EKG		X								
Echocardiogram		X				X	X		X	
MLWHFQ		X				X	X		X	
6-minute walk		X				X	X		X	
Cardiopulmonary Stress Test		X				X	X		X	
24 hour Holter Monitor		X				X	X			
Urine pregnancy test		X					X		X	
Eligibility determination		X								
Randomization		X								
OPTIMIZER™ System Implant*			X							
Chest X-ray*			X							
Optimizer Device Interrogation / Programming*			X	X	X	X	X	X	X	X
ICD Device Interrogation (episodes of VT/VF)				X		X	X	X	X	
Adverse Events, Hospitalizations, and Procedures (as needed) /OPTIMIZER device-related SAEs after 50-wks		X	X	X	X	X	X	X	X	X

[§] Study Start Date: After completion and satisfying all entry criteria, a date shall be scheduled for OPTIMIZER System implant. This date shall serve as the start date for all subjects. For subjects randomized to CCM Treatment, the OPTIMIZER system shall be implanted on this date. For subjects randomized to the Control group in whom an ICD implant is planned, the Study Start Date shall be the day of the ICD implant. For subjects randomized to the Control group who do not undergo an ICD implant, the scheduled implant shall be cancelled and this date shall serve as the Study Start Date from which all future follow-up visits are scheduled.

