* For subjects randomized to ACTIVE TREATMENT group. Subjects are followed every 6 months (+/- 4 weeks) after the 50-week interval for Optimizer Device Interrogation and safety reporting only (All deaths, and OPTIMIZER Device-related SAEs with the corresponding hospitalizations, procedures only).

The details of the Schedule of Events are provided in the **Section VI. A. Treatments to be administered.**

C. Anticipated Rate of Site and Patient Recruitment

Four hundred and eighteen (418) study participants will be recruited from an estimated 50 study sites.

D. Data Safety and Monitoring Board (DSMB)

An independent DSMB shall be established to review results and adverse events in order to provide unbiased oversight of the study. The DSMB shall be composed of members with clinical trial experience in heart failure, electrophysiology and statistics. The sponsor shall work with the DSMB to develop a set of standard operating procedures which shall include the timing and format of regularly scheduled meetings, the format in which data shall be submitted by the data coordinating center to the DSMB members and the format in which the DSMB shall transmit their findings to the Sponsor.

E. Event Adjudication Committee (EAC)

An EAC shall be established. The EAC will be responsible for the review, adjudication and validation of all reported SAEs that occur over the course of the study and the subsequent classification of these complications as related to the device or procedure. The committee shall also adjudicate the cardiac relatedness of deaths and hospitalizations. The EAC shall be composed of independent physicians not otherwise affiliated with the study. The committee will determine a schedule for meeting times based on the expected rate of patient accrual.

F. A description of the measures taken to minimize/avoid bias

This study has been designed to minimize sources of bias so that clinical device performance may be assessed clearly and objectively.

1. Site selection

The trial will be a multi-center study, with approximately 50 clinical sites located in the United States. Site selection will be based upon investigator and site experience in multi-center studies of heart failure treatments, adequate resources and availability of an appropriate patient population.

2. Randomization

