Following the 50 week follow up, subjects in the Control group shall resume routine follow-up from their primary care providers. Subjects in the Treatment group can continue to receive treatment with CCM signals. These patients shall be seen at ~6 month intervals at the investigational site. These follow-up visits shall include an Optimizer device interrogation and reporting of any Optimizer device-related serious adverse events (and corresponding hospitalizations and procedures, if any) and all deaths. These visits shall continue until FDA has made a determination of device safety and efficacy. In the event that the study is terminated prior to approval, the device is found to be ineffective or at the request of the patient, the device can be removed. Alternatively, the device can be left in place and deactivated; in this case, the device charger would be retrieved from the patient in order to eliminate the possibility of further use of the device.

f. Device retrieval in case of subject death

In the event that a study participant dies, every attempt will be made to secure permission from the family to retrieve the device.

In such cases, the device shall be shipped to the sponsor where it shall be inspected and interrogated.

B. Treatment of Subjects Enrolled in Phase I of this Study

Phase I of this study was designed as a double blind study in which all subjects underwent OPTIMIZER II System implant and were randomized for 6 months to either receive or not receive CCM treatment. This is then followed by a 6 month period of open label CCM treatment. Fifty patients were enrolled in this phase at 10 investigational sites. Treatment of patients enrolled in Phase I is further detailed in Appendix D. In brief, these patients shall be offered an OPTIMIZER III device when the battery of the OPTIMIZER II system becomes depleted.

C. Medications/treatments permitted (including rescue medication) and not permitted before and/or during the trial

Subjects will remain on their initial medication regimens throughout the study, unless clinical circumstances dictate a change. There are no restrictions on the types of medications that may be used during the trial.

D. Procedures for monitoring subject compliance

Clinical monitoring will be performed by/or under the management direction of the Impulse Dynamics Clinical Affairs Department.

VII. Assessment of efficacy

A. Specifications of efficacy parameters

The primary efficacy parameter shall be:

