The safety of the OPTIMIZER™ System will be assessed by evaluating the incidence and seriousness of adverse events (see section IX.A.2 for statistical analysis plan). The primary safety endpoint shall be the proportion of patients experiencing a composite event of all-cause mortality and all-cause hospitalization by the 12 month visit.

An adverse event is defined as any undesirable clinical occurrence in a subject, including death. Examples of adverse events that could occur as a result of the surgical procedure and implantation of the device components are listed below in hierarchical order of clinical severity:

1. Death
2. Arrhythmias (tachy- or bradycardias)
3. Stroke or transient ischemic attack (TIA)
4. Respiratory failure
5. RV perforation

6. Bleeding
7. Infection
8. Pleural and pericardial effusion
9. Pneumothorax

Examples of additional adverse events that could occur as a result of the subjects' underlying disease (i.e., heart failure) or CCM signal application are listed below in hierarchical order of clinical severity:

1. Abnormalities of cardiac function
2. Worsening of heart failure
3. Myocardial tissue damage
4. Chest pain

B. Serious, Device Related and Unanticipated Adverse Event Definitions.

Adverse events that occur during this study may be associated with the implant procedure, or specifically associated with the use of the device. An adverse event will be considered to be device-related when, in the judgment of the Principal Investigator, there is a logical connection between the use of the device and the occurrence of the event, above and beyond the study procedure itself.

A serious adverse event is any untoward medical occurrence that results in death, is life-threatening, requires inpatient hospitalization, prolongation of existing hospitalization or invasive treatment, results in persistent or significant disability/incapacity or is a congenital anomaly/birth defect. An unanticipated adverse device event is defined as any serious adverse effect on the health or safety of a subject or any life-threatening problem or death caused by or associated with the device, which was not listed in the Investigational Plan or the labeling for the device.

A serious device-related adverse event is any serious adverse event (as defined above) that is considered definitely related to the Optimizer System. An adverse event will be considered device-related when, in the judgment of the Principal

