Investigator, there is a logical connection between the use of the device and the occurrence of the event, above and beyond the study procedure itself. Examples include:

- Optimizer lead failure (dislodgement, fracture) requiring surgical revision
- Optimizer IPG failure requiring surgical revision
- Optimizer pocket erosion requiring surgical revision
- Pocket stimulation secondary to CCM, requiring surgical revision

C. Procedures for recording and reporting adverse events and intercurrent illnesses.

The Investigator shall report all adverse events to Impulse Dynamics and to the reviewing IRB (according to Hospital policy). All device malfunctions and serious adverse events, including, but not limited to events associated with prolongation of hospitalization, and/or a new hospitalization or death shall be reported to Impulse Dynamics within 24 hours of the Investigator learning of the event. Impulse Dynamics will report serious adverse events to the Data Safety and Monitoring Board (during the 1 year study only) and to the FDA as required.

D. Type and duration of follow-up of subjects after adverse events.

All subjects experiencing serious adverse events will be followed as required by their condition. Impulse Dynamics will investigate any anticipated or unanticipated serious adverse effect or subject death. If it is determined that the adverse event could present an unreasonable risk to other subjects, all investigations or parts of investigations presenting that risk will be terminated. Investigation of the event and notification of study termination will occur within five working days after notice of the effect is received at Impulse Dynamics. The terminated investigation will not be resumed without IRB approval.

IX. Statistical Considerations

A. Description of the statistical methods to be employed

1. Primary efficacy analysis

The primary efficacy analysis will compare responder rates between the Treatment and Control groups at the 6-month follow-up visit. The primary outcome measure will be:

- change from baseline in the ventilatory threshold (VT) determined on cardiopulmonary stress testing

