The OPTIMIZER II pulse generator will be replaced with the OPTIMIZER™ III rechargeable pulse generator, which is connected to the three leads placed during the initial implant procedure. The device replacement procedure is performed under sterile technique. Device interaction (if the patient has an ICD) and function is checked and a chest X-ray taken according to hospital policy to evaluate lead placement. Patients may be instructed on when and how to use the battery charger and will be discharged with the device turned on.

Patients will be asked to return to the hospital two weeks after the device replacement for a physical examination, a medication check, and device interrogation. Additional instruction on use of the battery charger will be provided as necessary.

Post Study Follow-Up

Following the 50 week follow up, subjects can continue to receive treatment with CCM signals. These patients shall be seen at ~6 month intervals at the investigational site. These follow-up visits shall include an Optimizer device interrogation and reporting of any Optimizer device-related serious adverse events (and the corresponding hospitalizations and procedures, if any) and all deaths. These visits shall continue until FDA has made a determination of device safety and efficacy. In the event that the study is terminated prior to approval, the device is found to be ineffective or at the request of the patient, the device can be removed. Alternatively, the device can be left in place and deactivated; in this case, the device charger would be retrieved from the patient in order to eliminate the possibility of further use of the device.

Consent Materials

A template consent for the Phase I Patients requesting a device exchange is attached.

A consent addendum is included in Appendix F to inform subjects with the OPTIMIZER III System of the modified follow-up requirements and the availability of the OPTIMIZER IVs System.

TABLE 1. Schedule of Events										Post-Randomization					
TEST	Screening	Baseline	Implant	Week 2 [§] ±2days	Week 4 [‡] ±2days	+4 ±1 wks	+12±1 wks	+22±1 wks	+24±1 wks	Device Exchange [†]	+2 wks ±2days [†]	36±2 wks	50±2 wks	Device Exchange ^{††}	Every 6 Months **
Informed consent	X									X*				X*	
Medical History	X			X	X	X	X		X		X	X	X		X
Physical Examination	X		X	X	X	X	X		X		X	X	X		
Medications	X		X	X	X	X	X		X		X	X	X		
NYHA Classification	X					X	X		X			X	X		
Echocardiogram		X					X		X				X		
MLWHFQ		X				X	X		X			X	X		

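### Section VIII.B sets two conflicting tests for a serious device-related event, and after week 50 that term decides which non-fatal events are collected

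*Combined protocol and SAP*

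**What the plan says.** Section VIII.B of the protocol states the relatedness test three times.

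- First, for any adverse event: it is device-related when, in the Principal Investigator's judgment, "there is a logical connection between the use of the device and the occurrence of the event".
- Second, for serious events: a serious device-related adverse event is "any serious adverse event (as defined above) that is considered definitely related to the Optimizer System".
- Third, in the sentence straight after that, the looser test returns, again left to site judgment: "Investigator, there is a logical connection between the use of the device and the occurrence of the event, above and beyond the study procedure itself". Four examples follow (lead failure, generator failure, pocket erosion, pocket stimulation), each needing surgical revision.

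The section defines no graded scale of relatedness and gives no order of precedence.

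The scope of reporting after week 50 is set elsewhere.

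- The Table 1 row reads "Adverse Events, Hospitalizations, and Procedures (as needed) /OPTIMIZER device-related SAEs after 50-wks", and its footnote limits later reporting to "All deaths, and OPTIMIZER Device-related SAEs with the corresponding hospitalizations, procedures only".
- Section VI.A.3.e asks for "reporting of any Optimizer device-related serious adverse events (and corresponding hospitalizations and procedures, if any) and all deaths".
- Appendix D asks the same of Phase I subjects: "reporting of any Optimizer device-related serious adverse events (and the corresponding hospitalizations and procedures, if any) and all deaths".
- Section VIII.C tells the investigator to report every adverse event, with serious events and device malfunctions due within 24 hours. It sets no relatedness condition and no end date.

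**The concern.** During the first 50 weeks a disagreement over relatedness changes how an event is labelled, but the event is still in the database. After week 50, under Table 1 and its footnote, relatedness decides whether a non-fatal serious event is collected at all. The term that does this work is the one defined in two ways.

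The other safeguards are weaker in that period:

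- The primary safety endpoint (Section IV.A.3) counts death or hospitalization from any cause, but stops at 12 months.
- Under Section VIII.C the sponsor forwards serious events to the DSMB during the one-year study only.
- The Event Adjudication Committee (Section IV.E) classifies relatedness for serious events that have been reported. It cannot reclassify an event that a site did not send.
- Control subjects return to routine care after week 50 (Section VI.A.3.e), so no concurrent group remains in which to see an excess.

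The events most exposed are those with more than one plausible cause. Hardware failures such as the four examples are usually easy to attribute. Arrhythmia and worsening heart failure can come from the signal or from the disease (Sections II.C.1 and VIII.A). The introduction to Section VIII also accepts that the mechanism of action is unknown, which makes certainty hard to claim.

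**Working it through.** The point rests on no power, rate or margin, so the check is a comparison of texts.

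**Step 1: which test applies to a serious event?** Section VIII.B supports both answers. The sentence that defines the serious category requires certainty. The next sentence, in the same paragraph and leading into serious examples, requires a logical connection. The two cannot both be the criterion.

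**Step 2: which reporting scope applies after week 50?** The documents again support two answers. Table 1 and its footnote, Section VI.A.3.e and Appendix D give a narrow scope. Section VIII.C gives a full scope with no time limit.

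**Step 3: combine them.** Take a non-fatal serious event after week 50 in an implanted subject, which the investigator thinks is logically connected with the device but not certainly caused by it.

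| Test used by the site | Scope used by the site | Event reported? |
|---|---|---|
| Logical connection | Table 1 footnote | Yes |
| Logical connection | Section VIII.C | Yes |
| Definite | Section VIII.C | Yes, but not counted as device-related |
| Definite | Table 1 footnote | No |

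One of four defensible readings loses the event, and another leaves it out of the device-related count. Two sites that both follow the protocol could therefore send different data.

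**Step 4: can the loss be sized?** Let N be the number of logically connected, non-fatal serious events after week 50 at sites on the fourth reading, and D the number of these judged definite. The share omitted is (N − D)/N. If D = N the share is 0%; if D = 0 it is 100%. The documents give neither N nor D. The nearest figure is from the FIX-HF-3 Extension study (Section II.B), where 14 of 43 adverse events were "definitely, possibly or probably related to the device". That figure pools the three grades and is not limited to serious events, so it does not narrow the range.

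**Step 5: who is exposed?** The documents give no count of subjects in follow-up after week 50. A ceiling for Phase II comes from the SAP: 215 were randomized to Optimizer, 7 never received study treatment (Section VII), and a further 4 refused treatment (Section X), so 215 − 7 − 4 = 204. Deaths, withdrawals and subjects who choose not to continue reduce this. Phase I subjects who received the OPTIMIZER III add to it.

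**The case against.** The strongest reply is that the paragraph explains itself. The logical-connection sentence comes straight after the strict one and before a list of serious events, so it can be read as saying how relatedness is judged for serious events too. A site that reads it so loses nothing. This stands, and it rules out a stronger claim that a reader might infer: that the protocol plainly applies its strictest test to its gravest events. The text is an unresolved contradiction, not one clear strict rule.

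A reader might also infer that this definition is the only filter after week 50, and that uncertain events can never reach adjudication. The documents do not support that. Section VIII.C still asks for serious events and device malfunctions within 24 hours, without an end date. The unanticipated-event definition in Section VIII.B covers harm associated with the device, without requiring certainty. Device interrogation continues about every six months. These routes are incomplete, however. The Table 1 footnote is more specific than Section VIII.C and excludes everything else, and the unanticipated-event route leaves out events already listed in the plan, which include arrhythmia and worsened heart failure.

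A third inference is that long-term counts could not be compared with the earlier program. The evidence is thin. The pooled three-grade count comes from one 14-subject extension study and covers all adverse events. The main FIX-HF-3 summary names no scale. The two accounts also differ: nine device-related events among 22 subjects in the main study, against twelve in the 14-subject subset over the same eight weeks. They show no single earlier standard.

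Finally, no planned or reported analysis uses data from after week 50, and Section IX.C treats the study as complete at about that point. This is correct and limits the weight of the point.

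**Conclusion.** The contradiction in Section VIII.B is real, and so is the conflict between Section VIII.C and the post-week-50 reporting rules. Together they allow a site to comply with the protocol and still omit non-fatal serious events that it considers logically connected with the device. The long-term count of device-related serious events would then depend on each site's reading.

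The effect is confined to descriptive surveillance of implanted subjects after week 50. Before then the risk is misclassification in a device-related count, not loss of the event. The primary safety result and the reporting of deaths do not depend on relatedness.

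The conclusion assumes that at least some sites follow the 'definitely' wording and the Table 1 footnote. The documents do not show how many do. Actual under-counting is therefore possible but not demonstrated, and the omitted share at such sites could be anywhere from 0% to 100%.

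**What to change.** 1. In Section VIII.B, delete 'definitely' from the definition of a serious device-related adverse event, so that the protocol's own logical-connection test applies to serious and non-serious events alike. This needs no new grading scale. The documents do not equate a logical connection with any set of grades, and the amendment need not do so.
2. State in Section VIII.B that this test triggers reporting after week 50.
3. Reconcile Section VIII.C with the Table 1 row and footnote, Section VI.A.3.e and Appendix D, by saying which reporting duties continue after week 50.

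The cost is a short amendment, a note to sites and a few more event reports. No analysis, sample size or visit changes.
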